7.3 Statistical Analyses for Efficacy

All efficacy endpoints will be summarized in the ITT population.

The ITT Population will be summarized by treatment group as randomized at the Baseline of Study M16-046.

Continuous variables will be summarized by the number of observations, mean, standard deviation, median, minimum, maximum, as well as the 95% confidence intervals (CIs) of the mean values. Categorical variables will be summarized by counts and percentages, as well as the 95% CIs of the percentages.

There will be no statistical testing for all of the efficacy and safety endpoints.

Efficacy assessments will be summarized by Observed Cases (OC) approach. No data imputation will be applied. Observed Cases will not include values after a subject prematurely discontinue from study drug.

Sample Size Estimation

Approximately 600 subjects that complete treatment in Study M16-046 will roll over in this open label treatment extension study. The sample size is determined by the completion of Study M16-046 and the consenting for the extension.

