4.0 Analysis Populations

Significant non-compliance was identified at a site. As a result of this finding, subjects enrolled in this site will not be included in any analysis population and data collected from this site will not be included in any analysis.

The following populations will be used for the analyses.

The Intent-to-Treat (ITT) Population consists of all enrolled subjects who receive at least one dose of study drug in the study and will be used for the efficacy analyses.

The Safety Population is the same as the ITT Population for this study. This population will be used to provide a comprehensive summary of safety.

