9.0 Efficacy Analyses

9.1 General Considerations

[figure not shown]
An Interim Analysis will be performed after all ongoing subjects have completed the Week 16 visit. The Final database lock will be performed at the end of study.

Efficacy variables will be summarized in the Study M19-850 ITT Population at each visit of Study M16-046 and Study M19-850, unless otherwise specified. No statistical testing will be performed.

A subject's M16-046 Baseline is defined as the last non-missing observation on or before their first dose of study drug in M16-046. For randomized but not treated subjects, the Baseline value will be the last non-missing measurement recorded prior to randomization. All efficacy endpoints defined below are relative to the M16-046 Baseline unless otherwise specified.

Efficacy assessments for ITT Population will be presented for the following three groups at each visit:

• subjects originally randomized to dupilumab in Study M16-046

- subjects originally randomized to upadacitinib in Study M16-046
- ITT Population (only applicable at visits of Study M19-850)

Continuous variables will be summarized by the number of observations, mean, standard deviation, median, minimum, maximum, 25th and 75th percentiles, as well as the 95% confidence intervals (CIs) of the mean values. Categorical variables will be summarized by counts and percentages, as well as the 95% CIs of the percentages.

The Observed Cases (OC) approach as defined in Section 9.2 will be used for all efficacy variables.

Analysis of Categorical Variables

For ITT Population, frequencies and percentages will be summarized along with 95% confidence interval (CI) based on normal approximation.

OC will be the only approach for categorical endpoints (Section 9.2).

Analysis of Continuous Variables

For ITT Population, the raw values at each visit and Baseline, change from Baseline/percent change from Baseline will be presented for the three treatment groups mentioned in this Section who have both Baseline and post-baseline visit values. The mean, 95% confidence interval, standard error, Min, Q1, median, Q3 and Max will be summarized.

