9.2 Handling of Missing Data

Missing data will be handled using the following methods for the efficacy analyses:

• Observed Cases (OC): The OC analysis will not impute values for missing evaluations, and thus a subject who does not have an evaluation on a scheduled visit will be excluded from the OC analysis for that visit. OC will exclude values after a subject prematurely discontinue from study drug + 1 days.

OC will be the only imputation method for all the efficacy endpoints.

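### Observed Cases is the only efficacy approach, so binary response rates labelled ITT describe subjects observed before premature discontinuation and are likely, not certainly, optimistic for the ITT Population

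*SAP*

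**What the plan says.** SAP 9.2 states that "OC will be the only imputation method for all the efficacy endpoints". Under it, "a subject who does not have an evaluation on a scheduled visit will be excluded from the OC analysis for that visit", and "OC will exclude values after a subject prematurely discontinue from study drug + 1 days". SAP 9.1 repeats that response endpoints have no other approach. Protocol 7.3 agrees: "No data imputation will be applied". Despite the SAP's phrase 'imputation method', OC imputes nothing.

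The population is wider than the set observed at a visit. SAP 4.0: "The Intent-to-Treat (ITT) Population consists of all enrolled subjects who receive at least one dose of study drug in the study". The same section removes every subject at one non-compliant site, so ITT means dosed subjects outside that site.

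For response endpoints SAP 9.1 plans the following: "Categorical variables will be summarized by counts and percentages, as well as the 95% CIs of the percentages". The intervals use the normal approximation. For continuous endpoints it also plans the number of observations. SAP 5.0 tabulates study drug discontinuation by reason.

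Protocol 5.4 to 5.6 govern who leaves. Systemic rescue means stopping study drug and leaving the study. Sustained EASI worsening makes discontinuation mandatory. Lack of response is a named reason for leaving. Anyone who stops study drug early is withdrawn from the study altogether.

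**The concern.** A subject who leaves for poor response counts as a non-responder at the visits already attended, then disappears from numerator and denominator at every later visit. The later rates therefore describe a group that is partly selected on outcome, under a label that refers to nearly everyone dosed. Long-term efficacy is part of the stated objective (Protocol 3.1, SAP 2.1), and a flat or rising response curve to Week 52 could partly reflect who left. The planned confidence intervals cover sampling error among observed subjects and say nothing about this. No supportive summary is planned that counts the subjects who are missing.

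**Working it through.** **Is the loss related to outcome?** Partly.
- Mandatory removal needs EASI worsening of at least 25%, that is EASI at or above 125% of the M16-046 Baseline, at two consecutive visits. EASI 75 needs EASI at or below 25% of that Baseline. Subjects in between can stay and count as non-responders, so the rule removes only the worst outcomes. Systemic rescue and withdrawal for lack of response add to this.
- Other loss need not depend on response. Subjects leave for adverse events or at their own request, and EASI cannot be scored at a remote COVID-19 visit (Protocol 5.10).
- The OC set is not the same as subjects on drug. Interruptions have no time limit (Protocol 5.8), and an interrupted subject who is assessed stays in OC.

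**Inputs.** N is about 600: "Approximately 600 subjects that complete treatment in Study M16-046 will roll over in this open label treatment extension study" (Protocol 7.3). That figure comes from roll-over and consent, not a formula, so there is nothing to reproduce. Every rate below is an assumption. Let p be the response rate in observed subjects, q the rate in missing subjects, and d the missing share.
- True rate in the ITT group = (1 − d)p + dq
- OC bias = p − true rate = d(p − q)
- Non-responder floor = p(1 − d)
- OC minus floor = pd
- Planned 95% CI half-width = 1.96 × √(p(1 − p)/n), with n = 600(1 − d)

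Results for p = 80% (gaps, biases and half-widths in percentage points):

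| d | n | Floor | Gap (= bias if q = 0) | Bias, q = 40% | Bias, q = 80% | Bias, q = 100% | CI half-width |
|---|---|---|---|---|---|---|---|
| 10% | 540 | 72% | 8 | 4 | 0 | −2 | 3.4 |
| 20% | 480 | 64% | 16 | 8 | 0 | −4 | 3.6 |
| 30% | 420 | 56% | 24 | 12 | 0 | −6 | 3.8 |

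For the same three values of d, the gap is 6, 12 and 18 points at p = 60%, and 9, 18 and 27 points at p = 90%.

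The bias exceeds the half-width when q < p − half-width/d:
- d = 10%: 0.80 − 0.0337/0.10 = 46%
- d = 20%: 0.80 − 0.0358/0.20 = 62%
- d = 30%: 0.80 − 0.0383/0.30 = 67%

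**Effect of separating COVID-19 missingness.** Take N = 600, 480 observed and 384 responders.
- OC = 384/480 = 80.0%. Strict floor = 384/600 = 64.0%.
- If 30 of the 120 missing are COVID-related, the counts are 384 responders, 186 non-responders and 30 COVID-missing (sum 600). Excluding the 30 gives 384/570 = 67.4%.
- If 60 are COVID-related, 384/540 = 71.1%.
- Counting those subjects as failures therefore lowers the figure by 3.4 or 7.1 points.

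**What can already be derived?** Responder counts are planned at each visit, and observed n for EASI and Worst Pruritus NRS appears in the continuous summaries. With the number treated, this gives responders/N for the full-ITT endpoints. For the dupilumab non-achiever subsets, SAP 9.1 also summarises the extension's ITT Population at M16-046 visits by randomised arm. Observed n minus responders in the Week 24 dupilumab-arm table therefore gives the subset N, apart from missing Week 24 values.

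**The case against.** The strongest reply is that nothing here is wrong. OC is stated openly and identically in both documents. Efficacy is exploratory, there is no primary or secondary efficacy endpoint, and nothing is tested. The denominators are largely recoverable, as shown above. A non-responder row is known to be pessimistic. With a true rate of 70% and 20% lost regardless of response, OC gives 0.56/0.80 = 70% and the floor gives 56%. It would also be added after the Week 16 interim and depart from the protocol's rule against imputation.

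Most of this stands, and it sets the priority low. It does not remove the gap: a reader must assemble several tables to see how far each printed rate falls short of the labelled population, and COVID-related missingness is not separated.

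A reader might go further and infer that the OC rates are certainly inflated, or that the ITT label makes the plan contradictory. The documents support neither. Bias is zero if missing subjects respond as observed ones do, and negative if they respond more often. The method is declared, and the population definition does not promise complete data.

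**Conclusion.** The point holds as a low-priority improvement. Binary response rates through Week 52 describe subjects observed before premature discontinuation. They are likely optimistic for the ITT Population because some withdrawal follows from poor response. They are not certainly so, because other missingness is unrelated to it.

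The documents give no dropout, response or COVID-missed rate, so the size is unknown. The 16-point gap at an assumed OC rate of 80% and 20% missing is the distance to a worst-case floor, not an estimate of bias. The bias equals that gap only if no missing subject responds.

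**What to change.** - Keep OC as planned and label it 'observed cases before premature discontinuation'. Print n observed/N beside each OC rate, where N is the ITT group or the endpoint's defined subset.
- Add to SAP 9.1/9.2 one supportive non-responder summary at M19-850 visits through Week 52. It may be limited to EASI 75/90/100, Worst Pruritus NRS improvement of at least 4, head-and-neck EASI 75, and the dupilumab non-achiever subsets.
- For regional endpoints, restrict N to subjects with regional EASI above 0 at M16-046 Baseline. Percent reduction is otherwise undefined.
- Count separately the visits missing because of COVID-19: missed or remote visits without a value, and visits after a COVID-related discontinuation. The supplemental forms in Protocol 6.1 record these. All other missing visits count as non-response. Give responders as % of N and as % of N minus the COVID count.
- Present the result as a conservative floor, not an unbiased estimate. Record it in SAP 14.0 as a change from Protocol 7.3 made after the interim (data cutoff 09MAR2021, SAP 12.0).

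No new data are needed, and continuous endpoints are unchanged. The cost is SAP wording and modest programming. All binary endpoints would need 8 full-population endpoints × 6 visits × 3 groups + 8 subset endpoints × 6 visits = 144 + 48 = 192 rows. The limited set drops three body regions (3 × 6 × 3 = 54 rows), leaving 138. The statistical downside is a floor that can lie further from the truth than OC when loss is unrelated to response. If only one step is taken, the label with n observed/N removes the main risk of misreading.

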9.3 Primary Efficacy Endpoints and Analyses

9.3.1 Primary Efficacy Endpoints

There is no primary efficacy endpoint for this study.

9.3.2 Main Analysis of Primary Efficacy Endpoints

This section is not applicable since there is no primary endpoint in this study.

9.3.3 Sensitivity and Supplementary Analyses of the Primary Efficacy Endpoints

This section is not applicable since there is no primary endpoint in this study.

9.4 Secondary Efficacy Endpoints and Analyses

9.4.1 Key Secondary Efficacy Endpoints

There is no secondary efficacy endpoint for this study.

9.4.2 Main Analyses of Key Secondary Efficacy Endpoints

This section is not applicable since there is no secondary endpoint in this study.

9.4.3 Sensitivity and Supplementary Analyses for Key Secondary Efficacy Endpoints

This section is not applicable since there is no secondary endpoint in this study.

9.4.4 Supportive Secondary Efficacy Endpoints and Analyses

This section is not applicable since there is no secondary endpoint in this study.

9.5 Additional Efficacy Analyses

Other efficacy endpoints are listed in Section 3.3. The analysis detail is specified in Section 9.1.

[figure not shown]
The following endpoints will be summarized only at the visits of Study M18-850.

- Proportion of subjects achieving 75% reduction in EASI in the head and neck body region among subjects who received dupilumab in Study M16-046 and did not achieve 75% reduction in EASI in the head and neck body region at Week 24 of Study M16-046;
- Proportion of subjects achieving 75%/90%/100% reduction in EASI (EASI 75/90/100) among subjects who received dupilumab in Study M16-046 and did not achieve EASI 75 at Week 24 of Study M16-046;
- Proportion of subjects achieving EASI 90/100 among subjects who received dupilumab in Study M16-046 and did not achieve EASI 90 at Week 24 of Study M16-046;
- Proportion of subjects achieving EASI 100 among subjects who received dupilumab in Study M16-046 and did not achieve EASI 100 at Week 24 of Study M16-046;
- Proportion of subjects achieving an improvement (reduction) in Worst Pruritus NRS reduction ≥ 4 among subjects who had Worst Pruritus NRS ≥ 4 at Baseline, received dupilumab in Study M16-046 and did not achieve Worst Pruritus NRS reduction ≥ 4 at Week 24 of Study M16-046.

Missing data will be imputed as specified in Section 9.2.

9.6 Efficacy Subgroup Analyses

There will be no efficacy subgroup analyses in this study.

10.0 Safety Analyses

10.1 General Considerations

Safety data will be summarized for the Safety Population. Safety summaries will include data collected from the first dose of updacitinib in Study M16-046 or Study M19-850, whichever is earlier.

All the safety related endpoints will be summarized for the following three groups, unless otherwise specified:

- Subjects originally randomized to dupilumab in Study M16-046 and continued in Study M19-850
- Subjects originally randomized to upadacitinib in Study M16-046 and continued in Study M19-850
- All the subjects dosed in Study M19-850

For laboratory and vital sign tables, only the first two groups will be included.

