5.8 Study Drug

The study drug information is presented in Table 2.

Table 2. Description of Study Drug

Investigational Product	Mode of Administration	Formulation	Strength	Manufacturer
Upadacitinib (ABT-494) tablet	oral	Film-coated tablet	30 mg	AbbVie

The type and amount of kits dispensed will be managed by the Interactive Response Technology (IRT).

AbbVie will not supply drugs other than upadacitinib.

In cases of state of emergency or pandemic situations, study drug shipment can be made from the study site to the subject if allowed by local regulations. Refer to the Operations Manual Appendix F for details on direct-to-patient (DTP) shipment of study drug.

There are no time limits for study drug interruption if no permanent study discontinuation criteria have been met.

Storage and Disposition of Study Drug

Upadacitinib tablets must be stored at controlled room temperature (15° to 25°C/59° to 77°F).

The investigational product is for investigational use only and are to be used only within the context of this OLE study. The investigational product supplied for this study must be maintained under adequate security and stored under the conditions specified on the label until dispensed for subject use or destroyed on site as appropriate.

Upon receipt, study drug should be stored as specified on the label and kept in a secure location. Each kit will contain a unique kit number. This kit number is assigned to a subject via IRT and encodes the appropriate study drugs to be dispensed at the subject's corresponding study visit. Study drugs must not be dispensed without contacting the IRT system. Study drugs will only be used for the conduct of this study.

Packaging and Labeling

Upadacitinib tablets will be packaged in bottles with quantities sufficient to accommodate the study design. Each bottle will be labeled per local requirements. The labels must remain affixed to the bottles. Each kit label will contain a unique kit number.

Dispense Study Drug

The type and amount of kits dispensed will be managed by the IRT. Upadacitinib tablets will be dispensed through IRT beginning at Baseline (Day 1) according to dispensation schedule in Appendix D.

The first dose of study drug will be administered after all other Baseline (Day 1) procedures are completed. At the visits specified, the site personnel will review returned study drug kits and empty study drug packaging to verify compliance.

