Such an event can result from use of the drug as stipulated in the protocol or labeling, as well as from accidental or intentional overdose, drug abuse, or drug withdrawal. Any worsening of a pre-existing condition or illness is considered an AE. Worsening in severity of a reported AE should be reported as a new AE. Laboratory abnormalities and changes in vital signs are considered to be AEs only if they result in discontinuation from the study drug, necessitate therapeutic medical intervention, meets protocol specific criteria (see Section 6.2 regarding toxicity management) and/or if the investigator considers them to be AEs.

The investigators will monitor each subject for clinical and laboratory evidence of AEs at each visit throughout the study. All AEs will be followed to a satisfactory conclusion.

If any of the following events are reported, then the following supplemental report must be completed (Table 4).

Table 4. Supplemental Electronic Case Report Forms

Adverse Event	Supplemental Form
Cardiac events Myocardial infarction or unstable angina Heart failure Cerebral vascular accident and transient ischemic attack Venous thromboembolism	Cardiovascular (Cardiac) AE eCRF Myocardial Infarction and Unstable Angina AE eCRF Heart Failure Adverse Event eCRF Cerebral Vascular Accident and Transient Ischemic Attack AE eCRF Embolic and Thrombotic Event (Non-Cardiac, Noncentral nervous system [CNS]) eCRF
Herpes Zoster Infection	Herpes Zoster AE eCRF
ALT/AST > 3 ULN	Hepatic Abnormal Laboratory Value Supplemental eCRF Hepatic Supplemental Local Labs eCRF (if applicable) Hepatic Supplemental Procedure eCRF (if applicable)
Serum creatinine > 1.5 × the Baseline value and > ULN Serum creatinine ≥ 2.0 mg/dL	Renal Abnormal Laboratory Value Supplemental eCRF Renal Supplemental Local Labs eCRF (if applicable) Renal Supplemental Procedure eCRF (if applicable)
Creatine kinase (CPK) value ≥ 4 × ULN and no symptoms suggestive of myositis or rhabdomyolysis CPK ≥ 4 × ULN accompanied by symptoms suggestive of myositis or rhabdomyolysis CPK increases considered by the investigator to be an AE	Increased CPK Supplemental eCRF
Acne	Acne eCRF
Death	Death eCRF
Eczema herpeticum (or the synonymous Kaposi's varicelliform eruption)	Eczema herpeticum eCRF

AE = adverse event; ALT = alanine aminotransferase; AST = aspartate aminotransferase; CPK = creatine phosphokinase; eCRF = electronic case report form; ULN = upper limit of normal

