All AEs reported from the time of study drug administration through 30 days after the last dose of study drug administration will be collected, whether solicited or spontaneously reported by the subject.

Additionally, in order to assist the adjudication process, additional information on any potential major adverse cardiovascular events will be collected, if applicable.

Adverse event information will be collected as shown in Figure 2.

Figure 2. Adverse Event Collection

- * Any AEs occurring prior to the first dose of Study M19-850 should be considered as AEs for Study M16-046, regardless of when the consent form is signed.
- ** Any AEs occurring on or after the first dose of Study M19-850 should be considered as AEs for Study M19-850.

AbbVie will be responsible for Suspected Unexpected Serious Adverse Reactions (SUSAR) reporting for the Investigational Medicinal Product (IMP) in accordance with global and local requirements. A SUSAR is an adverse reaction of which the nature or severity is not consistent with the applicable product information such as investigator's brochure.

Adverse events will be monitored throughout the study to identify any of special interest that may indicate a trend or risk to subjects.

Adverse Events of Special Interest

The following AESI will be monitored during the study:

- Serious infections
- Opportunistic infections
- Herpes zoster
- Active Tuberculosis
- Malignancy (all types)
- Adjudicated Gastrointestinal perforations
- Adjudicated cardiovascular events (e.g., major adverse cardiovascular event [MACE])
- Anemia
- Neutropenia
- Lymphopenia
- Renal dysfunction
- Hepatic disorders
- Elevated CPK

- Adjudicated embolic and thrombotic events (non-cardiac, non-central nervous system).
- COVID-19 (consider while pandemic is ongoing).

Adverse Event Severity and Relationship to Study Drug

The investigators will rate the severity of each AE according to the National Cancer Institute (NCI) Common Terminology Criteria for Adverse Events (CTCAE) version 5.0.

If no grading criteria are provided for the reported event, then the event should be graded as follows:

Mild (Grade 1) Asymptomatic or mild symptoms; clinical or diagnostic observations only;

intervention not indicated

Moderate (Grade 2) Minimal, local or noninvasive intervention indicated; limiting age-

appropriate instrumental activities of daily living (ADL)

Severe (Grade 3 - 5)

Grade 3 Severe or medically significant but not immediately life-threatening;

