7.4 Statistical Analyses for Safety

Safety will be assessed by AEs, physical examination, laboratory assessments, and vital signs. Note that missing safety data will not be imputed. Analysis details will be specified in the SAP.

Adverse events will be coded using the Medical Dictionary for Regulatory Activities (MedDRA). Treatment-emergent adverse events are defined as those that began or worsened in severity after the first dose of study drug and no more than 30 days after the last dose of the study drug. The number and percentage of subjects experiencing TEAEs will be tabulated using the MedDRA SOC and PT, by severity, and by relationship to the study drug as assessed by the investigator. Summaries (including percentages and events per 100 patient-years) of SAEs, deaths, AEs leading to discontinuation, and AESI will be provided as well.

For laboratory and vital signs, mean change from Study M16-046 Baseline and percentage of subject with evaluations meeting criteria for pre-defined Potentially Clinically Significant values will be summarized.

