1.0 Introduction

This Statistical Analysis Plan (SAP) describes the statistical analyses for upadacitinib Study Protocol M19-850, A Phase 3b, open-label treatment extension study of upadacitinib for the treatment of adult subjects with moderate to severe atopic dermatitis who completed treatment in Study M16-046.

Study M19-850 examines the long-term safety, tolerability and efficacy of upadacitinib in adult subjects with moderate to severe atopic dermatitis who successfully completed treatment in Study M16-046.

The SAP will not be updated in case of administrative changes or amendments to the protocol unless the changes impact the analysis.

Unless noted otherwise, all analyses will be performed using SAS Version 9.4 (SAS Institute Inc., Cary, NC 27513) or later under the UNIX operating system.

This SAP includes changes to analyses described in the protocol. Details are outlined in Section 14.0.

[figure not shown]

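### If SAP patient-years start at the first upadacitinib dose in either study, rates of death, AE discontinuation and rollover-barring AESIs include about 24 weeks in which rollovers could hardly have had those events

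*SAP*

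**What the plan says.** SAP 10.1 sets the safety window: "Safety summaries will include data collected from the first dose of updacitinib in Study M16-046 or Study M19-850, whichever is earlier". SAP 10.2.1 defines TEAEs on the same basis, through 30 days after the last upadacitinib dose.

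SAP 10.2.4 divides the number of TEAEs by total patient-years taken from the duration in SAP 6.0, and SAP 10.2.6 plans AESI rates per 100 patient-years. The 6.0 duration is last minus first upadacitinib dose date, plus 1. That sentence names no study. The opening of 6.0 places the summary in M19-850, but its exposure categories start at the first upadacitinib dose in either study and run to 160 weeks or more.

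Under SAP 4.0 the Safety Population is everyone dosed in M19-850. Protocol 5.1 (items 1 and 3) requires these subjects to have completed M16-046 treatment without a permanent discontinuation criterion. The listed criteria include active TB, GI perforation, and malignancy other than localized NMSC or cervical carcinoma in situ.

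Protocol 7.4 promises the rates at issue: "Summaries (including percentages and events per 100 patient-years) of SAEs, deaths, AEs leading to discontinuation, and AESI will be provided as well". On timing it says: "Treatment-emergent adverse events are defined as those that began or worsened in severity after the first dose of study drug". Protocol 6.1 allocates events between the studies: "Any AEs occurring prior to the first dose of Study M19-850 should be considered as AEs for Study M16-046", and "Any AEs occurring on or after the first dose of Study M19-850 should be considered as AEs for Study M19-850".

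**The concern.** Subjects randomized to upadacitinib in M16-046 (the upadacitinib-origin group) enter the cumulative rates only if they survived and stayed on drug to the end of M16-046. Their M16-046 time is therefore immortal time for death and AE discontinuation, and very nearly so for the three AESIs that bar rollover. It adds to the denominator and can add almost nothing to the numerator.

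SAEs (which include deaths), AEs leading to discontinuation and AESI are primary safety endpoints (SAP 3.1). No testing is planned, so the descriptive rates are the result. The error is towards lower rates, in the upadacitinib-origin and all-subjects columns. The dupilumab-origin column beside them has no upadacitinib lead-in, so the columns would differ even if the M19-850 rates were equal. SAP 10.6 plans no other safety analysis that would show this.

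**Working it through.** **Inputs**
- Lead-in: 24 weeks (SAP 2.2; M19-850 Baseline is Week 24 of M16-046).
- M19-850 treatment: 52 weeks at all sites, with safety visits up to Week 136 in the listed countries (SAP 2.2).
- About 600 subjects (SAP 2.4).
- Assumed, because the documents do not give them: mean M19-850 exposure W, here 52 to 136 weeks and the same in both origin groups; upadacitinib-origin share p, here 0.5 with range 0.4 to 0.6.

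**Which denominator?** The highest category in SAP 6.0 is reproduced by 24 + 136 = 160 weeks. The rows for at least 148 and at least 160 weeks cannot be reached within 136 M19-850 weeks, so those categories count M16-046 upadacitinib time. This favours the cumulative reading, although 6.0 does not state it for the duration used in 10.2.4.

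**Reading A: cumulative patient-years.** With the same events in the numerator, the planned rate is below the rate over M19-850 patient-years by:
- upadacitinib-origin: 24/(24+W)
- all subjects: 24p/(24p+W)

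| | W = 52 | W = 136 |
|---|---|---|
| Upadacitinib-origin | 24/76 = 32% | 24/160 = 15% |
| All subjects, p = 0.5 | 12/64 = 19% | 12/148 = 8% |
| All subjects, p = 0.4 to 0.6 | 16% to 22% | 7% to 10% |

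These are ratios of person-time and need no constant-hazard assumption.

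Example: assume 300 upadacitinib-origin subjects and 10 AE discontinuations.
- 52 weeks is 300 × 52 × 7/365.25 = 299.0 PY; 76 weeks is 437.0 PY. The rate is 10/437.0 = 2.29 instead of 10/299.0 = 3.34 per 100 PY.
- 136 weeks is 781.9 PY; 160 weeks is 919.9 PY. The rate is 1.09 instead of 1.28.

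A constant-hazard simulation (true rate 5.0 per 100 PY, 52 weeks) gave 4.98 over the M19-850 window, 3.38 over the SAP window in rollovers, and 4.99 when all M16-046 upadacitinib starters were counted. The rollover condition causes the gap; cumulative exposure as such does not.

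**Sensitivity to onset dating.** Suppose the comparison rate counts only AEs with onset in M19-850, and k of the 10 discontinuation AEs began in M16-046. At W = 52 the gap is 1 − (10/76)/((10−k)/52):
- k = 0: 31.6%
- k = 1: 1 − 520/684 = 24.0%
- k = 2: 1 − 520/608 = 14.5%
- k = 4: 520/456 = 1.14, so the planned rate is the higher one.

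**Reading B: M19-850 patient-years only.** The five categories are not diluted. M16-046 events of other types are then divided by M19-850 time, which overstates the upadacitinib-origin rate by 24r/W, where r is the M16-046 rate over the M19-850 rate.

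| r | W = 52 | W = 136 |
|---|---|---|
| 0.5 | 23% | 9% |
| 1 | 46% | 18% |
| 2 | 92% | 35% |

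**Duplicate day.** SAP 10.2.4 adds one day to a duration that already includes it: 600/365.25 = 1.64 PY, or 0.22% of 735.9 PY (600 subjects, equal split, W = 52). This is immaterial.

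**The case against.** The cumulative window is deliberate. It appears in SAP 6.0, 10.1 and 10.2.1 and fits the aim of long-term upadacitinib safety. No estimand names an M19-850-only rate as the target. That rate is also conditional on rollover, and it ignores 24 weeks of earlier exposure, which matters for events of long latency. All of this stands, and it is why the cumulative tables should stay. It does not restore the events that the rollover condition removes from those 24 weeks.

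A reader might infer that the SAP makes an unlogged departure from the protocol. Protocol 5.8 does place the first dose at M19-850 Baseline ("The first dose of study drug will be administered after all other Baseline (Day 1) procedures are completed"), and SAP 1.0 says: "This SAP includes changes to analyses described in the protocol. Details are outlined in Section 14.0". Section 14.0 has no entry for this window. But protocol 7.4 names no study in its TEAE definition and leaves details to the SAP, and the 6.1 notes govern which study an AE belongs to. The supplied protocol also lacks the Week 136 extension that the SAP describes, so a later amendment was not seen. Section 14.0 is a version history and would not show text present since version 1.0. A departure is plausible but not shown.

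A reader might also infer that all safety rates are diluted. The documents do not support that. Other TEAEs, SAEs and AESIs can have M16-046 events in the numerator. Thromboembolic events are not named in the protocol 5.1 list.

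The onset-dating objection also stands for discontinuations. The rule "Worsening in severity of a reported AE should be reported as a new AE" limits how many AEs carry over, but not AEs that persist unchanged, which protocol 5.10 says are followed in M19-850.

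**Conclusion.** The point holds conditionally. On the better-supported reading of SAP 6.0, the planned upadacitinib-origin rates for TEAEs leading to death, TEAEs leading to discontinuation, active TB, GI perforation and malignancy excluding NMSC are about 15% to 32% below the same events over M19-850 patient-years, for W from 136 down to 52 weeks. With an equal split the all-subjects rates are 8% to 19% below. For the three AESIs the figures are close rather than exact, because the malignancy exemption and entry deviations leave small gaps. Against an onset-dated comparison, the discontinuation gap can shrink or reverse.

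On the other reading these five categories are sound and the remaining TEAE rates are overstated. Neither reading gives sound rates throughout, so the text needs to change either way. Because primary safety rates are affected and the remedy is cheap, this should be fixed.

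**What to change.** 1. State in SAP 6.0 and 10.2.4 that the cumulative patient-years start at the first upadacitinib dose in either study. Label those rates as conditional on completing M16-046 and rolling over.
2. Add to 10.2.4 and 10.2.6 rates over M19-850 patient-years for the five categories, and base conclusions on these categories on the added rates.
   - Death and discontinuation: keep the SAP's own TEAE numerator, since in rollovers these outcomes necessarily fall after M16-046 treatment. Apply no 30-day cut to the date of death, so that later deaths from a TEAE, which 10.2.2 still summarizes, are not lost. Flag AEs with M16-046 onset.
   - The three AESIs: count onset from the first M19-850 dose to 30 days after the last dose.
3. Housekeeping: record the cumulative window in Section 14.0, and delete the duplicate day in 10.2.4.

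The cost is SAP wording, an onset flag and one extra table set from existing data. The downside is two rates per category, which need clear labels. No planned table is lost.
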